11.22 Evaluation of target visceral lesions or target lymph nodes

11.223 Identification of target lesions

- Measurable lesions (as defined in Section 11.1) up to a maximum of 5 representative of all involved organs, should be identified as “Target Lesions” and recorded and measured at baseline.
- Target visceral lesions and target lymph nodes should be selected on the basis of their size, be representative of all involved sites of disease, but in addition should be those that lend themselves to reproducible repeated measurements. It may be the case that, on occasion, the largest lesion (or malignant lymph node) does not lend itself to reproducible measurements in which circumstance the next largest lesion (or malignant lymph node) which can be measured reproducibly should be selected.

11.224 Measurement Methods

- All measurements should be recorded in metric notation (i.e., decimal fractions of centimeters) using a ruler or calipers.
- The same method of assessment and the same technique must be used to characterize each identified and reported lesion at baseline, at the end of cycle 4 and at the end of treatment.

11.225 Acceptable modality

- Tumor imaging will be performed using a full body PET-CT. If the site can document that the CT performed as part of a PET-CT is of identical diagnostic quality to a diagnostic CT (with IV and oral contrast), then the CT portion of the PET-CT can be used for RECIST measurements.

11.226 Evaluation of target lesions

- Baseline Sum of Dimensions (BSD): A sum of the longest diameter for all target visceral lesions plus the sum of the short axis of all the target lymph nodes will be calculated and reported as the baseline sum of dimensions (BSD). The BSD will be used as reference to further characterize any objective tumor response in the measurable dimension of the disease.
- Post-Baseline Sum of the Dimensions (PBSD): A sum of the longest diameter for all target visceral lesions plus the sum of the short axis of all the target lymph nodes will be calculated and reported as the post-baseline sum of dimensions (PBSD). If the radiologist is able to provide an actual measure for the target visceral lesion (or target lymph node), that should be recorded, even if it is below 0.5 cm. If the target visceral lesion (or target lymph node) is believed to be present and is faintly seen but too small to measure, a default value of 0.5 cm should be assigned. If it is the opinion of the radiologist that the target visceral lesion or target lymph node has likely disappeared, the measurement should be recorded as 0 cm.

- The minimum sum of the dimensions (MSD) is the minimum of the BSD and the PBSD.

11.227 Measurement of effect

- Complete Response (CR): All of the following must be true:
 - a. Disappearance of all visceral lesions.
 - b. Each target lymph node must have reduction in short axis to <1.0 cm.
- Partial Response (PR): At least a 30% decrease in PBSD (sum of the longest diameter for all target visceral lesions plus the sum of the short axis of all the target lymph nodes at current evaluation) taking as reference the BSD (see Section 11.226).
- Progression (PD): At least one of the following must be true:
 - a. At least one new malignant lesion, which also includes any lymph node that was normal at baseline (<1.0 cm short axis) and increased to ≥1.0 cm short axis during follow-up.
 - b. At least a 20% increase in PBSD (sum of the longest diameter for all target visceral lesions plus the sum of the short axis of all the target lymph nodes at current evaluation) taking as reference the MSD (Section 11.41). In addition, the PBSD must also demonstrate an absolute increase of at least 0.5 cm from the MSD.
- Stable Disease (SD): Neither sufficient shrinkage to qualify for PR, nor sufficient increase to qualify for PD taking as reference the MSD.

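### Read literally, the MSD includes the sum being judged, so target-lesion regrowth after a response is not PD under criterion (b) until it is 20% and 0.5 cm above baseline

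*Combined protocol and SAP*

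**What the plan says.** Section 11.226 defines three quantities for target visceral lesions and lymph nodes.

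- **BSD**, the baseline sum, is the reference for response: "The BSD will be used as reference to further characterize any objective tumor response in the measurable dimension of the disease".
- **PBSD** is the same sum after baseline. It "will be calculated and reported as the post-baseline sum of dimensions (PBSD"), and the section does not say which post-baseline visit or visits are meant.
- **MSD**: "The minimum sum of the dimensions (MSD) is the minimum of the BSD and the PBSD".

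Section 11.227 then gives the progression rule: "Progression (PD): At least one of the following must be true". Route (a) is "At least one new malignant lesion, which also includes any lymph node that was normal at baseline" and has since reached 1.0 cm in short axis. Route (b) is "At least a 20% increase in PBSD", where PBSD is explained as the sum "at current evaluation) taking as reference the MSD (Section 11.41"). Route (b) also requires that "the PBSD must also demonstrate an absolute increase of at least 0.5 cm from the MSD".

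Section 11.41, cited there for MSD, gives only the schedule and recording of mSWAT for skin lesions.

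Imaging is scheduled at baseline, after cycle 4 and at end of treatment (Section 4.1 footnote 4; Section 11.224).

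**The concern.** The same symbol stands on both sides of the comparison in route (b). If PBSD is the current sum, as Section 11.227 explains it, then MSD is the smaller of the baseline sum and the current sum. A sum below baseline is compared with itself, and a sum above baseline is compared with baseline. The sum recorded after cycle 4 plays no part in the end-of-treatment decision. A patient whose nodes or visceral lesions shrink and then regrow is judged as if the shrinkage had not happened. The only pointer offered for MSD leads to the skin section, so it cannot settle what was meant.

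What is at stake is secondary. Section 11.5 makes the absence of nodal or visceral progression a condition of overall systemic response, and Section 16.42 lists that proportion for reporting. Two people coding the rule could give the same scans different statuses.

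**Working it through.** The plan states no figure that depends on MSD, so there is nothing to reproduce. The check applies route (b) under two readings.

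**Inputs from the plan.** A rise of at least 20% over MSD and of at least 0.5 cm over MSD (Section 11.227); response as a fall of at least 30% from BSD (Section 11.227); one baseline and two scheduled post-baseline scans. The tumour sums below are illustrative assumptions.

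**Rule.** With current sum C, route (b) is met if C ≥ 1.2 × MSD and C − MSD ≥ 0.5 cm.

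- Literal reading: MSD = min(BSD, C).
- Smallest-earlier-sum reading: MSD = min(BSD, all PBSDs before C).

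**Step 1: the literal reading in general.** If C ≤ BSD, then MSD = C, the increase is 0, and route (b) fails. A search over baseline and current sums from 0.05 to 20 cm found no exception. If C > BSD, then MSD = BSD. So the literal threshold is always max(1.2 × BSD, BSD + 0.5 cm). The two terms are equal at BSD = 2.5 cm, and above that the 20% term governs.

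**Step 2: example.** BSD 8.0 cm, after cycle 4 3.0 cm, end of treatment 6.0 cm.

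- Literal: MSD = min(8.0, 6.0) = 6.0; increase (6.0 − 6.0)/6.0 = 0%. The fall from baseline is (8.0 − 6.0)/8.0 = 25%, short of partial response. Status: stable disease.
- Smallest earlier sum: MSD = 3.0; increase (6.0 − 3.0)/3.0 = 100%, and 3.0 cm. Status: PD.
- Literal PD threshold: max(1.2 × 8.0, 8.0 + 0.5) = 9.6 cm.
- Smallest-earlier-sum threshold: max(1.2 × 3.0, 3.0 + 0.5) = 3.6 cm.

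End-of-treatment sums from 3.6 cm to just under 9.6 cm are therefore PD on one reading and not on the other. At 5.5 cm the literal rule even gives partial response, since (8.0 − 5.5)/8.0 = 31%, although the sum has risen (5.5 − 3.0)/3.0 = 83% from its low point.

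**Step 3: regrowth needed for literal PD.**

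| Low point as share of BSD | BSD ≥ 2.5 cm | BSD = 1.5 cm |
|---|---|---|
| 70% | 1.2/0.7 − 1 = +71% | 2.0/1.05 − 1 = +90% |
| 50% | 1.2/0.5 − 1 = +140% | 2.0/0.75 − 1 = +167% |
| 30% | 1.2/0.3 − 1 = +300% | 2.0/0.45 − 1 = +344% |

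For BSD = 1.5 cm the threshold is max(1.8, 2.0) = 2.0 cm.

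**Step 4: when the readings can differ.** At the scan after cycle 4 the only earlier sum is BSD. If C ≤ BSD, neither reading gives PD by route (b); if C > BSD, both use BSD. They agree. They can differ only at the end-of-treatment scan or a later unscheduled one.

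**Step 5: which endpoints use the result.** The primary endpoint uses mSWAT only (Sections 11.0 and 16.11), so it does not change. Overall systemic response uses nodal and visceral progression directly (Section 11.5). Section 16.42 ends progression-free survival at relapse or death, and duration of response at relapse; Section 11.211 defines relapse for skin only. Section 16.42 does refer to progression when censoring progression-free survival, so a link exists only if nodal or visceral progression is counted as an event.

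**The case against.** The strongest reply is that a running minimum was meant. Section 11.226 does not tie PBSD to one visit, and more than one PBSD can exist. The reference to the current visit occurs only in Section 11.227, where it may simply pick out which PBSD is being tested. On the literal reading MSD does no work, because comparison with BSD would give the same result. This is persuasive about intent, and a running minimum is probably what the authors wanted. It does not rescue the wording: the stated formula, coded with the only explanation of PBSD that the progression rule supplies, gives the wrong status.

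A reader might infer that regrowth after a response can never be scored as progression. The documents do not support that. Even on the literal reading, regrowth to max(1.2 × BSD, BSD + 0.5 cm) is PD, and a new malignant lesion is PD without any use of MSD.

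A reader might also infer that progression-free survival and duration of response are inflated. That is only possible, given that both are worded around relapse. Where PD has already been declared on skin, Section 13.2 places the end-of-treatment visit and restaging at that PD, and the scan cannot remove the event.

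The number of patients affected may also be zero. Section 3.13 allows measurable disease by mSWAT alone, accrual stops at 10, and the readings differ only for a patient whose target lesions shrank, then regrew within the window above, with no new lesion. This stands, and it is why the point is minor.

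**Conclusion.** Wrong as written; minor severity. Taken literally, Sections 11.226 and 11.227 do not score target-lesion regrowth after a nodal or visceral response as PD under route (b) until the sum is at least 20% and at least 0.5 cm above baseline. In the 8.0/3.0/6.0 cm example that turns PD into stable disease and moves the threshold from 3.6 to 9.6 cm.

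The effect is confined to the end-of-treatment scan or a later unscheduled one. The primary endpoint and the interim rule are untouched. Overall systemic response can be misclassified; with 10 evaluable patients, one such patient who also has the required skin response would move that proportion by 1/10, or 10 percentage points. This assumes that the end-of-treatment staging feeds the endpoint. Section 11.5 names no time point, but the notes ahead of Section 1.0 do use that staging to identify non-responders. Effects on progression-free survival and duration of response depend on whether nodal or visceral progression is an event, which Section 16.42 leaves unclear. The documents do not say how many patients have target nodal or visceral lesions, so no expected number can be given.

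**What to change.** For endpoint scoring, replace the MSD sentence in Section 11.226 with: MSD is the smallest of the BSD and all PBSDs recorded before the current evaluation. In Section 11.227, change the cross-reference for MSD from Section 11.41 to Section 11.226.

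The cost is one sentence and one section number. No new data, scans or visits are needed, and sums already recorded can be rescored. Because Sections 7.1 and 13.2 also use progression to end treatment, the sponsor should confirm that those passages and the scoring rule are consistent; this point takes no position on the treatment rule.

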11.1 Definitions of Measurable

11.11 Measurable Disease

- 11.111 A primary cutaneous lesion is measurable if detectable through standard full body skin examination. Documentation by color photography is required.
- 11.112 A visceral lesion is considered measurable if its longest diameter can be accurately measured as 2.0 cm with chest x-ray, or as ≥ 1.0 cm with CT scan, CT component of a PET/CT, or MRI.
- 11.113 A malignant lymph node is considered measurable if its short axis is ≥ 1.5 cm when assessed by CT scan (CT scan slice thickness recommended to be no greater than 5 mm).

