11.5 Overall Objective Status

Overall systemic response rate is defined as 50% or greater reduction of baseline mSWAT score without evidence of progressive nodal, visceral, or blood involvement.

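### Section 11.227 has no progression rule for nodes and visceral lesions that are present at baseline but are not targets, so their growth defaults to stable disease and can pass as systemic response under Section 11.5

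*Combined protocol and SAP*

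**What the plan says.** **Which lesions are measured.** Section 11.113 sets the threshold for nodes: "A malignant lymph node is considered measurable if its short axis is ≥ 1.5 cm when assessed by CT scan". Under 11.112 a visceral lesion is measurable on CT from a longest diameter of 1.0 cm. Section 11.223 takes as targets "Measurable lesions (as defined in Section 11.1) up to a maximum of 5 representative of all involved organs".

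**What counts as progression.** Section 11.227 requires at least one of two conditions.
- Route (a): "At least one new malignant lesion, which also includes any lymph node that was normal at baseline (<1.0 cm short axis", continuing "and increased to ≥1.0 cm short axis during follow-up".
- Route (b): the sum over target lesions rises by at least 20% and at least 0.5 cm above its minimum.

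Stable disease is what remains when neither PR nor PD is met.

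**Where it is used.** Section 11.5 defines systemic response as at least a halving of baseline mSWAT "without evidence of progressive nodal, visceral, or blood involvement". Section 16.42 lists the proportion with overall systemic response among its secondary response rates. Section 11.5 does not say which rule decides whether nodal or visceral involvement is progressive. Section 11.227 is the only written rule for those sites.

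**The concern.** The size thresholds do not meet. A node counts as normal below 1.0 cm and can be a target from 1.5 cm. A diseased node between those sizes at baseline is not new, not normal and not in the target sum. The same holds for a sixth measurable lesion and for a visceral lesion too small to measure on CT. Section 11 has no non-target category for judging progression, so this disease can grow without limit and still be classed as stable.

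The gap can be reached in practice. Criterion 3.13 accepts measurable disease by mSWAT alone. A patient who enters on skin disease and has only nodes of 1.0 to <1.5 cm has no extracutaneous target, so route (b) has no sum to work on.

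At stake is the systemic response proportion, the one secondary response rate that is meant to show that skin improvement is not accompanied by progression elsewhere.

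**Working it through.** The documents give no figure for this point, so the check applies the rules literally to worked cases.

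**Inputs**
- Node is a target only if baseline short axis b ≥ 1.5 cm (11.113, 11.223), with at most five targets (11.223).
- Route (a): a new malignant lesion, or b < 1.0 cm with follow-up f ≥ 1.0 cm (11.227).
- Route (b): (PBSD − MSD)/MSD ≥ 20% and PBSD − MSD ≥ 0.5 cm, with sums over targets only (11.226, 11.227). At the first post-baseline scan with growth, MSD equals the baseline sum.
- Systemic response: mSWAT reduction ≥ 50% and no progressive nodal, visceral or blood involvement (11.5).

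**Uncovered range for nodes.** Not normal means b ≥ 1.0, and not a target means b < 1.5. Nodes with 1.0 ≤ b < 1.5 cm are therefore outside both routes.

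**Cases** (all nodes recorded as diseased at baseline)

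| Case | Change | Route (a) | Route (b) | Result |
|---|---|---|---|---|
| Sole target node 1.5 → 2.0 cm | +0.5 cm; 0.5/1.5 = +33% | no | yes | PD |
| Sole target node 1.5 → 4.0 cm | +2.5 cm; 2.5/1.5 = +167% | no | yes | PD |
| Node 1.0 → 4.0 cm | +3.0 cm | no | not in sum | not PD |
| Node 1.2 → 4.0 cm | +2.8 cm; 2.8/1.2 = +233% | no | not in sum | not PD |
| Node 1.4 → 4.0 cm | +2.6 cm | no | not in sum | not PD |
| Target node steady at 2.0 cm, plus node 1.2 → 4.0 cm | target sum 2.0 → 2.0 cm, 0% | no | no | SD |
| New malignant lesion | – | yes | – | PD |

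In the sixth case, had the second node been in the sum, the total would go from 2.0 + 1.2 = 3.2 cm to 2.0 + 4.0 = 6.0 cm. That is +2.8 cm, or 2.8/3.2 = +87.5%, well past both parts of route (b). The classification turns on target status alone.

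**Effect on 11.5.** Give the patient in the sixth case an mSWAT reduction of 50% or more and no progression in blood. Nodal status by 11.227 is SD, so the patient is a systemic responder.

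**Size.** Accrual stops at 10 patients (16.1, 16.31). One patient scored wrongly changes the proportion by 1/10 = 10 percentage points if all 10 are evaluable.

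**The case against.** The strongest reply is that 11.5 does not name 11.227. It asks for the absence of evidence of progressive involvement, and nothing in it forces a reader to ignore a 4 cm node. An investigator could call that node progressive by judgement. This stands as a condition on the conclusion. It does not close the gap, because a secondary endpoint would then rest on unwritten discretion that differs from the only written rule.

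A second reply is that a 1.2 cm node not regarded as malignant at baseline, but malignant at 4 cm, can be read as a new malignant lesion. That is fair. The example is certain only for a node recorded as diseased at baseline.

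Several stronger readings are tempting, and the documents do not support them:
- *Only targets and nodes below 1.0 cm can ever progress.* No: route (a) also counts any new malignant lesion. The gap concerns disease already present at baseline.
- *Non-target disease is ignored altogether.* No: the CR rule requires all visceral lesions to disappear, not only targets.
- *PFS is biased.* Not shown: 16.42 defines the event as relapse or death, words censoring in terms of progression, and does not cite 11.227. The only definition of relapse is cutaneous (11.211).
- *Loose nodal CR and PR criteria distort the response rates.* No: 16.42 assigns response on mSWAT, and 11.5 uses only the absence of progression.
- *RECIST 1.1 supplies or contradicts the missing rule.* The documents invoke RECIST for measurable disease at entry (3.13) and for measurement on the CT portion of PET-CT (11.225). Section 11.227 sets its own progression rule.

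**Conclusion.** The point holds. Applied as written, 11.227 classes growth of baseline non-target disease as stable, whatever its extent, and no other section supplies a rule for it. If 11.227 is what decides progressive involvement under 11.5, a patient with such growth and at least a 50% mSWAT reduction is counted as a systemic responder.

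The conclusion assumes that the node or lesion was recorded as diseased at baseline, that no new lesion appears, and that the target sum does not itself progress. The error runs one way: it can only add systemic responders.

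The size is about 10 percentage points per misclassified patient among 10. How many patients have such disease is not stated, so no expected bias can be given. The primary endpoint is cutaneous response by mSWAT (16.11) and does not change. This should be corrected, but it does not threaten the main result.

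**What to change.** For scoring the 11.5 endpoint only:
1. At baseline, record the extracutaneous disease that is not a target: diseased nodes of 1.0 to <1.5 cm, measurable lesions beyond the five targets, and visceral lesions under 1.0 cm on CT.
2. On the PET-CT reads already scheduled after Cycle 4 and at end of treatment (4.1), count unequivocal progression of that disease as progressive nodal or visceral involvement.
3. Cite this rule in 11.5, so that the systemic response proportion in 16.42 has one stated definition.

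PD also governs the stopping of treatment (7.1, 13.2). The sponsor should reconcile the endpoint definition with those passages and say whether they use the same definition. No treatment rule is proposed here.

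The cost is a few lines of wording and one non-target entry on the imaging form. No extra scans or readers are needed.

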11.3 Evaluation of peripheral blood

T and B-cell Quantitation will be utilized to evaluate peripheral blood. CD4 and CD8 test results will be collected and the ratio CD4:CD8 will be compiled.

11.31 Measurement effect

- Complete Response (CR): No blood involvement.
- Partial Response (PR): 50% decrease in CD4 count or CD4:CD8 ratio ≤10 .
- Progressive Disease (PD): 50% increase from baseline ($\geq5,000$ CD4+cells in blood or CD4:CD8 ratio ≥15).
- Stable Disease (SD): Not CR, PR or PD.

11.4 Measurement at Follow-up Evaluations

11.41 Cutaneous lesions

- mSWAT will be collected at baseline, end of every cycle of treatment and during clinical follow-up at 30 and 90 days.
- mSWAT response will be recorded as per Section 11.211.

11.42 Target visceral lesions and lymph nodes.

- Subsequent PET-CT scans must be obtained after cycle 4 and the end of treatment visit following initial documentation of objective cutaneous response status of either complete response (CR) or partial response (PR).
- In the case of stable disease (SD), follow-up measurements must have met the SD criteria at least once after study entry at a minimum interval of 3 weeks.
- The cytological confirmation of the neoplastic origin of any effusion that appears or worsens during treatment when the measurable tumor has met criteria for response or stable disease is mandatory to differentiate between response or stable disease (an effusion may be a side effect of the treatment) and progressive disease.

11.43 Peripheral blood

T and B-Cell Quantitation will be performed at baseline, end of cycle 4, and at end of treatment.

11.5 Overall Objective Status

Overall systemic response rate is defined as 50% or greater reduction of baseline mSWAT score without evidence of progressive nodal, visceral, or blood involvement.

12.0 Descriptive Factors

12.1 None.

13.0 Treatment/Follow-up Decision at Evaluation of Patient

Reason Off Treatment (from the Off Treatment Form)	Go to CFU, SFU, or end folder rollout
1 = Treatment (Intervention) Completed Per Protocol Criteria	CFU
2 = Patient Withdrawal/Refusal After Beginning Protocol Therapy (Intervention)	SFU
3 = Adverse Events/Side Effects/Complications	SFU
4 = Disease Progression, Relapse During Active Treatment (Intervention)	SFU
5 = Alternative Therapy	No follow-up
6 = Patient Off-Treatment (Intervention) For Other Complicating Disease	SFU
7 = Death On Study	No follow-up
8 = Other	SFU
10 = Disease Progression Before Active Treatment (Intervention)	No follow-up
24 = Patient Withdrawal/Refusal Prior To Beginning Protocol Therapy (Intervention)	No follow-up

13.1 Continuation of treatment

Patients who are CR90, PR, or SD will continue treatment per protocol up to a maximum duration of 24 months..

13.2 Progressive disease (PD)

Patients who develop PD (non-responders) during cycle 1 will exit the study (no follow-up). Patients who develop PD subsequent while receiving therapy will complete the End of Treatment visit at the time of PD and repeat staging per protocol, then proceed to survival follow-up (Section 4.2).

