4.2 Survival Follow-up

	Survival Follow-up				
	q. 3 months until PD	At PD	After PD q. 3 months	Death	New Primary
Survival Follow-up	X	X	X	X	At each occurrence

1. If a patient is still alive 2.5 year after registration, no further follow-up is required.

5.0 Stratification Factors OR Grouping Factor:

None.

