13.3 Off protocol treatment

Patients who do not develop PD during cycle 1 and go off protocol treatment for reasons other than PD within any cycle will proceed to survival follow-up. Note: This does not apply to patients receiving alternative therapy. Patients who go off treatment for alternative therapy will exit the study (no follow-up).

Patients who achieve CR at any time will proceed to survival follow-up.

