16.4 Analysis Plan

16.41 Primary Outcome Analysis: The mSWAT score at baseline and cycle 9 will be used for change in baseline calculations. All calculated values will use the last-observation-carried forward for any participants who withdraw, are lost to follow up, or exit the study per protocol. The proportion of successes will be estimated by the number of successes divided by the total number of evaluable patients will be analysed using Mann-Whitney U for nonparametric data and the student t-test. Confidence intervals for the true success proportion will be calculated according to the approach of Duffy and Santner (Duffy D 1987).

16.42 Secondary Outcome Analysis: These analyses will include all patients meeting the eligibility criteria who have signed a consent form and have begun treatment, including patients who fail to achieve a complete or partial response.

Adverse Events: All eligible patients that have initiated treatment will be considered evaluable for assessing adverse event rate(s). The maximum grade for each type of adverse event will be recorded for each patient, and frequency tables will be reviewed to determine patterns. Additionally, the relationship of the adverse event(s) to the study treatment will be taken into consideration.

Response Rates:

Changes in mSWAT scores from baseline will be evaluated at cycle 9. Summary statistics will be calculated.

Patients will be assigned response based on the mSWAT criteria in section 11.0. Proportions of patients will be calculated and described using summary statistics. Proportions of interest are patients having CR, CR90 and PR; patients having stable subcutaneous disease; patients having progressive cutaneous disease; and patients having an overall systemic response rate.

Progression free survival time is defined for all evaluable patients as the time from registration to relapse or death due to any cause. Patients are censored if they have not achieved a progression at the time of analysis. The distribution of progression-free survival will be estimated using the method of Kaplan-Meier. In addition, the progression-free survival rate at 5 years after registration will be reported.

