Duration of response is defined for all evaluable patients who have achieved a CR, CR90 or PR as the date at which the patient's objective status is first noted to be a CR, CR90 or PR to the earliest date relapse is documented. The distribution of duration of complete response will be estimated using the method of Kaplan-Meier.

Time to response is defined as the time from registration to CR, CR90 or PR. The distribution of survival time will be estimated using the method of Kaplan-Meier (Kaplan and Meier 1958).

Overall survival time is defined as the time from registration to death due to any cause. Patients are censored if they are alive at the time of analysis. The distribution of survival time will be estimated using the method of Kaplan-Meier (Kaplan and Meier 1958). In addition, the overall survival rate at 2 years after registration will be reported.

Additional Analyses: All endpoints may be analysed using patient characteristics to explore possible associations of demographics with the endpoints. Possible characteristics include clinical stage, gender and prior treatments.

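### Two groups of dosed patients leave with no follow-up (cycle-1 progressors under 13.2, against code 4 of the 13.0 table; patients off treatment for alternative therapy under 13.3), yet 16.42 counts them in overall survival

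*Combined protocol and SAP*

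**What the plan says.** **Cycle-1 progressors.** Section 13.2: "Patients who develop PD (non-responders) during cycle 1 will exit the study (no follow-up"). Progression in a later cycle leads to an end-of-treatment visit and then survival follow-up. Section 13.3 carries the same cycle-1 exception, since it sends to survival follow-up "Patients who do not develop PD during cycle 1 and go off protocol treatment for reasons other than PD within any cycle". The Section 13.0 table has the line "4 = Disease Progression, Relapse During Active Treatment (Intervention"), with survival follow-up as its destination and no cycle limit.

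**Alternative therapy.** Section 13.3: "Patients who go off treatment for alternative therapy will exit the study (no follow-up"). Code 5 of the 13.0 table says the same.

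**The follow-up schedule.** Section 4.2 sets three-monthly contacts before progression, a contact at progression and three-monthly contacts after it. It ends with: "If a patient is still alive 2.5 year after registration, no further follow-up is required".

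**The analysis.** Section 16.42 sets its population as follows: "These analyses will include all patients meeting the eligibility criteria who have signed a consent form and have begun treatment". OS runs from registration to death from any cause, is estimated by Kaplan-Meier, and is reported as a rate at 2 years. The one OS censoring rule is: "Patients are censored if they are alive at the time of analysis". By contrast, the primary analysis in 16.41 carries the last observation forward "for any participants who withdraw, are lost to follow up, or exit the study per protocol".

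**The concern.** There are two separate faults. First, staff handling a patient who was dosed and then progressed in cycle 1 have two opposite instructions. Second, the OS analysis includes patients for whom the plan schedules no vital-status contact, and it does not say how they enter the estimate.

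Kaplan-Meier treats a censored patient as having the same later risk as those still followed. Here release is triggered by progression or by a move to other therapy, so that assumption is open to doubt. The direction of any error is unknown, and the data that would settle it are not scheduled to be collected.

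**Working it through.** **1. Which patients are caught.** Drug is given on Day 1 of each cycle (7.1), so a patient who progresses during cycle 1 has normally been dosed and, if eligible, is in the 16.42 population. Code 10 of the 13.0 table (progression before active treatment) does not cover this patient; code 4 does. For alternative therapy the text and the table agree, so the mismatch there is only with 16.42. Patients who stop for later progression, adverse events, withdrawal after starting therapy or other reasons go to survival follow-up. Section 13.7 requires survival follow-up even for ineligible patients who were never treated, although they are outside the OS population.

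**2. What safety reporting still captures.** Inputs: treatment starts at most 28 days after registration (6.6). Deaths from any cause are reportable for 90 days after cessation, or 30 if new anticancer therapy starts (10.84). I count cessation from the single dose.

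- No new therapy: 28 + 90 = day 118 after registration; 730 − 118 = 612 days to the 2-year mark without required reporting of unrelated deaths.
- New therapy started: 28 + 30 = day 58; 730 − 58 = 672 days.

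These limits apply only to deaths not considered treatment-related. Related deaths are reportable with no end date (10.52, 10.6232, 10.81, 10.84). However, 10.81 does not require investigators to look for events in former participants.

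**3. Width of the undetermined range.** Let N be the number of patients, d the known deaths by 2 years, and k the released patients of unknown 2-year status. The 2-year proportion lies between (N − k − d)/N, if all k died, and (N − d)/N, if all k lived. The width is k/N. With N = 10 (16.31 after Amendment 4), it is 10 points for k = 1, 20 for k = 2 and 30 for k = 3, whatever the time of exit.

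**4. What Kaplan-Meier would report.** Assumed for illustration: N = 10, one exit censored when it happens, and deaths at months 8 and 16 among the other nine. True 2-year OS is 7/10 = 70% if the released patient dies by 2 years, and 8/10 = 80% if not.

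| Exit at | Kaplan-Meier at 24 months | Minus 70% | Minus 80% |
|---|---|---|---|
| 3 weeks or 6 months | (8/9)(7/8) = 77.8% | +7.8 | −2.2 |
| 12 months | (9/10)(7/8) = 78.8% | +8.8 | −1.3 |
| 18 months | (9/10)(8/9) = 80.0% | +10.0 | 0.0 |

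**5. For scale.** The exact 95% interval for 8 of 10 is 44% to 97%.

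**6. How often cycle-1 exit could occur.** Imaging and T/B-cell counts first come after cycle 4 (4.1, 11.43). Before cycle 2 the scheduled disease assessments are mSWAT, physical and dermatology exams, and photography (4.1). New tumors count as cutaneous progression, but a rise in mSWAT judged to be treatment inflammation or unmasking is classed as stable disease (11.211).

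**The case against.** The strongest reply is materiality. OS is secondary and descriptive, with no decision rule, in a trial cut to 10 patients whose power and type I error 16.1 already sets aside. The number of exits is unknown and probably small in cycle 1, the death times in the illustration are assumed, and sampling error is far larger than the effect of one exit. All of this stands. It limits the weight of the point but does not remove the contradiction or supply the missing rule.

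Kaplan-Meier also accepts censored patients, so the analysis can be run. That is true, but 16.42 does not say when a patient of unknown status is censored, and running the estimate does not make the censoring uninformative.

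A footnote ahead of Section 1.0 ties non-responders to repeat staging after cycle 4 and at end of treatment, which could bear on whom 13.2 means. The material it annotates is not available here, so it cannot settle the matter. Section 13.2 names cycle 1 explicitly.

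Three stronger readings are tempting and not supported:

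- *A reader might infer that no death after day 118 would be reported.* Treatment-related deaths remain reportable at any time.
- *A reader might infer that starting any new therapy ends follow-up.* Code 5 applies only when alternative therapy is the recorded reason off treatment, and 9.52 prohibits no therapy in post-treatment follow-up.
- *A reader might infer that reported OS will be too high.* The illustration gives errors in both directions, and the documents do not show which would occur.

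**Conclusion.** The point holds and should be fixed. Section 13.2 contradicts code 4 for dosed cycle-1 progressors. For them and for patients released under 13.3 and code 5, the follow-up plan does not supply what the OS analysis in 16.42 uses, and no censoring rule fills the gap. The size is up to 10 percentage points of 2-year OS per released patient of unknown status, assuming all 10 patients are in the analysis. This measures sensitivity to an exit; it is not an expected bias, because the documents do not give the number of exits.

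The primary endpoint is not affected: 16.41 has a rule for patients who exit, and they stay in its denominator. A cycle-1 progressor's progression event is also already recorded. Unlike the sampling error, this loss of information is avoidable.

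**What to change.** 1. Reconcile 13.2 with code 4 of the 13.0 table.
2. Amend 13.2, 13.3 and code 5 so that every patient who received a dose enters the existing Section 4.2 survival follow-up, subject to consent.
3. State in 16.42 that OS is censored at the date last known alive.
4. If any patient has already been released, report how many, and give best- and worst-case bounds for 2-year OS beside the Kaplan-Meier estimate. The bounds show the loss but do not recover it.

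The cost is a protocol amendment with IRB approval, possible re-consent (the consent pages are not available to check), and at most about 30/3 = 10 three-monthly status contacts per released patient. No clinic visit is added.
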